5.2.3 TICE BCG + PANVAC™ ARM

5.2.3.1 Enroll into study with baseline evaluation and studies as described in Section 3.4. Of note, there will be at least a 3 week delay from the time a previous bladder biopsy/TURBT to allow for adequate bladder healing prior to enrollment.

5.2.3.2 Week 0 (+/- 7 days) – all subjects in this arm receive single vaccinia priming vaccine - rV-PANVAC™ 2 x 10⁸ pfu SQ after undergoing phlebotomy with 6 green top tubes for immunologic correlates.

5.2.3.3 Weeks 3-8: Receive weekly (+/- 2 days) intravesical doses of BCG (TICE strain, 50 mg) as per usual standard of care for a total of 6 weeks. Urine will be tested weekly prior to each BCG administration and the presence of gross hematuria or evidence of a urinary tract infection will result in holding that week's BCG dose and postponing therapy until the following week. Also, at the beginning of each administration, patients will be queried about urinary symptoms.

- Complaints of persistent dysuria, urgency, bladder spasms, and/or frequency from previous week's administration that is consistent with Grade 3 or greater toxicity will result in holding BCG administration for that week, supportive care (e.g. medications and hydration), and/or BCG dose reduction (BCG can be given 1/3rd of the normal dose on the following week as this can result in less toxicity with similar results for recurrence and progression³¹).
- Subjects will be maintained at this reduced dose if they tolerate therapy.
- Future inability to tolerate this reduced dose will result in holding BCG for that week and postponing the BCG until the following week and dropping to 1/6 of the normal dose as this dose may still be effective in prolonging progression-free and cancer-specific survival times.³²

5.2.3.4 PANVAC administration will continue as planned regardless of any delays in BCG administration. Research sample collection of urine will coincide with the first and third week of BCG instillation regardless of any delays with BCG administration. Research sample collection of blood will coincide with the first and sixth week of BCG instillation regardless of any delays with BCG administration. [For example, if BCG is first given on week 3 of the study, but held on week 4 and resumed on week 5, then

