urine collection would be collected on weeks 0, 3, 6 (previously week 5), 18-21 (previously 17-20), and optionally on follow-up visits. In this scenario, blood would be collected on weeks 0, 3, 9 (previously week 8), 18-21 (previously 17-20), and optionally on follow-up visits. The timing of PANVAC administration will NOT change in this scenario.] Week (+/- 7 days) 3, 7, 11, and 15 – all patients in this arm receive boost fowlpox vaccines - rF-PANVACTM 1 x 10⁹ pfu SQ

- 5.2.3.5 Blood and urine will be obtained for correlative studies as described in Section 10.1.
- 5.2.3.6 Between weeks 17-20 (+/- 7 days), a CT urogram and chest x-ray prior to biopsy, a planned cystoscopy, EUA, and TURBT will be done of previous tumor area and of any new areas of tumor. Tissue will be sent for pathology and be formalin-fixed paraffin embedded. If possible, some tissue will also be frozen.
- 5.2.3.7 Also at the time of the end-of-study cystoscopy, urine will be collected for cytology and for immune-related markers along with blood for correlative aims.

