6 DOSING DELAYS/DOSE MODIFICATIONS

6.1 TICE BCG

The need for BCG dose modification may arise and has been described previously. To review, subjects will receive weekly (+/- 2 days) intravesical doses of BCG (TICE strain, 50 mg) as per usual standard of care for a total of 6 weeks. Urine will be tested weekly prior to each BCG administration and the presence of gross hematuria or a urinary tract infection by urinalysis will result in holding that week's BCG dose and postponing therapy until the following week. Also, at the beginning of each administration, subjects will be queried about urinary symptoms. Complaints of persistent dysuria, urgency, bladder spasms, and/or frequency from previous week's administration that is consistent with Grade 3 or greater toxicity will result in holding BCG administration for that week, supportive care (e.g. medications and hydration), and/or BCG dose reduction the following week at 1/3 normal dose as this can result in less toxicity with similar results for recurrence and progression.³¹ Complaints of non-infective cystitis or hematuria consistent with Grade 2 or higher will result in holding BCG administration for that week. Therapy will resume the following week at if these symptoms are at less than or equal to Grade 1. Subjects will be maintained at this reduced dose if they continue to fail to tolerate full dose therapy.

Future inability to tolerate this reduced dose will result in holding BCG for that week and postponing the BCG until the following week and dropping to 1/6 of the normal dose (details in Section 5.2). Of note, weekly BCG postponement or dose reductions will not alter the vaccination schedule. For example, if the week 5 dose of BCG is withheld, the subject will still receive the next dose of PANVAC™-F on week 7, but the last dose of BCG would be given on week 9 instead of week 8 (assuming that no other BCG postponement is necessary).

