10.1.3 Blood

For the BCG alone arm, blood samples for research analysis will be obtained

- at week 0 or at randomization by 1 10cc purple top tube
- prior to treatment at weeks 3 and 8 by 2 10cc red top tubes and 6 10cc green top tubes
- at the end of study (between weeks 17-20) by 1 10cc purple top tube, 2 10cc red top tubes and 6 10cc green top tubes.

For the BCG + PANVAC vaccine arm, blood samples for research analysis will be obtained

- at week 0 by 1 10cc purple top tube
- prior to treatment at weeks 0, 3, 8, 11, and 15 by 2 10cc red top tubes and 6 10cc green top tubes
- at the end of study (between weeks 17-20) by 1 10cc purple top tube, 2 10cc red top tubes and 6 10cc green top tubes.

Blood may also be collected on follow-up visits for up to 12 months following end of study cystoscopy. No more than 10.5 mL/kg or 550 mL, whichever is smaller, will be obtained from adult subjects over an 8-week period. The studies and method of storage for these specimens are described in Sections **10.1.5** and **10.2**.

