10.1.7.2 PBMCs, sera, and urine

The following time points will be analyzed: baseline (prior to vaccination in vaccination arm), week 3 (prior to BCG for both arms), week 8 (prior to last BCG for both arms), and at end of study (between weeks 17-20).

PBMCs

All patients who have the HLA-A2 allele will be analyzed by ELISPOT for CD8 T-cell responses specific for CEA, MUC-1, and a cascade antigen Brachyury. All samples will be evaluated for CD4 responses specific for CEA protein. All immune assays will have appropriate antigen controls. All PBMC samples will be analyzed by flow cytometry using 10 markers for each of the following cell types: CD4, CD8, Tregs, MDSCs, and NK.

- Satisfactory analytical performance characteristics of individual antibodies or affinity ligands for use in ELISPOT, flow cytometry, or ELISA will be demonstrated prior to analyses of the proposed protein markers, cytokines and chemokines.
- Analyses of sera samples for quantitation of antibodies to CEA, MUC-1 and a cascade antigen Brachyury will be described in detail to show clinically recapitulated tumor-associated antigens, including glycosylated proteins, are used in measuring autoantibodies in sera.

Background: Our studies in the LTIB have demonstrated the ELISPOT assay for IFN- γ production to be quantitative and reproducible as a measure of human T-cell responses to vaccination (26). The continued use of one reproducible assay has been instrumental in our ability to evaluate and compare patients' immune responses using different vaccines and vaccine strategies in the same institution, and among different cancer centers. ELISPOT assays employing the CEA agonist peptide and the MUC-1 agonist peptide have already been developed.

Sera

Sera samples at all time points will be analyzed for the development of antibodies to CEA, MUC-1, and a cascade antigen Brachyury.

Urine

Urine samples may be collected at baseline and at the end of therapy (week 17-20) for the presence of cytokines and chemokines. In addition, an effort will be made to collect urine at the time of BCG instillation #1 and #3 to assess for cytokine production in response to BCG therapy (as described earlier in section **10.1.2** and in Section **17.5** (Appendix E)).

For patients at CINJ, research samples consisting of urine (week 0, week 3, week 5, and week 17-20) will be drawn. These tubes will be further processed as per Appendix E, Section **17.5** and then shipped via Fed-Ex to [name] lab:

[name]

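### Section 5.2.3.4 conflicts with other sections on the PANVAC arm's research blood: if BCG 1 is held, the 'week 3' sample can follow the first boost, and the worked example omits weeks 11 and 15

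*Combined protocol and SAP*

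**What the plan says.** Section 5.2.3.4 sets two rules for the BCG + PANVAC arm. Blood follows BCG: "Research sample collection of blood will coincide with the first and sixth week of BCG instillation regardless of any delays with BCG administration". The vaccine does not: "PANVAC administration will continue as planned regardless of any delays in BCG administration". Section 6.1 repeats the second rule: "weekly BCG postponement or dose reductions will not alter the vaccination schedule". The fowlpox boosts are due at "Week (+/- 7 days) 3, 7, 11, and 15". Under Section 5.2.3.3, urine is tested before every instillation, and gross hematuria or evidence of infection "will result in holding that week's BCG dose and postponing therapy until the following week".

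Section 5.2.3.4 then works through a case in which BCG is given in week 3, held in week 4 and resumed in week 5. In that case "blood would be collected on weeks 0, 3, 9 (previously week 8), 18-21 (previously 17-20), and optionally on follow-up visits".

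The sampling plan in Section 10.1.3 asks for this arm's blood "prior to treatment at weeks 0, 3, 8, 11, and 15 by 2 10cc red top tubes and 6 10cc green top tubes", plus an end-of-study draw between weeks 17 and 20. Section 10.1.5, Calendar A in Section 11 and the blood protocol in Appendix E give the same weeks. Section 10.1.7.2 lists the time points to be analysed as baseline, "week 3 (prior to BCG for both arms), week 8 (prior to last BCG for both arms"), and end of study.

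**The concern.** Blood in this arm is drawn largely to follow responses to the vaccine antigens and to the cascade antigen Brachyury (objectives 1.3.5, 1.3.6 and 1.3.8), together with immune-cell profiles (1.3.7). For those measures, what matters about a sample is which vaccine doses came before it and how long ago. Section 5.2.3.4 lets the draws move while the doses stay put.

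The sample most exposed is the one labelled week 3. As planned, it is the only one that shows the effect of the vaccinia prime alone. If it is taken after the first boost, it carries the same label but describes a different exposure. Section 10.1.7.2 would not flag this, because it defines the sample only as preceding BCG.

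The worked example raises a separate problem. A coordinator who follows it literally for a patient with a hold would not collect the week 11 and week 15 blood, although four other places in the protocol require it.

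**Working it through.** There is no power or error-rate calculation to redo. The check is to trace the schedule.

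**Inputs.** Six weekly instillations start in week 3, and each held week pushes the remaining ones back by a week (5.2.3.3). Blood is drawn at instillations 1 and 6, and urine at 1 and 3 (5.2.3.4). Boosts are fixed at weeks 3, 7, 11 and 15 (5.2.3.4, 6.1). Windows are +/- 7 days for vaccine and +/- 2 days for BCG (5.3.2).

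**Reproducing the plan's example (hold in week 4).** BCG falls in weeks 3, 5, 6, 7, 8 and 9. The third instillation is in week 6 and the sixth in week 9. End of study moves from 17-20 to 18-21. This matches the urine and blood weeks in the example.

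**Comparing the blood lists.**

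| Source | PANVAC-arm blood weeks |
|---|---|
| 10.1.3, 10.1.5, Calendar A, Appendix E | 0, 3, 8, 11, 15, 17-20 |
| Example, week 4 hold | 0, 3, 9, 18-21 |
| Example with the omitted draws restored | 0, 3, 9, 11, 15, 18-21 |

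The blood-volume limit in 10.1.3 does not explain the omission. By Appendix E, the week 0 and end-of-study draws are 10 + 20 + 60 = 90 mL each, and the others are 20 + 60 = 80 mL. With the draws restored, the heaviest 8-week span (weeks 11, 15 and 18) is 80 + 80 + 90 = 250 mL. The limit is 550 mL or 10.5 mL/kg, whichever is smaller, and 250 / 10.5 = 23.8 kg, so the weight limit would bind only below that body weight.

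**Moving the hold.**

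| BCG held in week(s) | First blood | Weeks after week 3 boost | BCG 6 blood | Weeks after week 7 boost |
|---|---|---|---|---|
| none | 3 | 0 | 8 | 1 |
| 4 | 3 | 0 | 9 | 2 |
| 3 | 4 | 1 | 9 | 2 |
| 3, 4 | 5 | 2 | 10 | 3 |
| 3, 4, 5 | 6 | 3 | 11 | 4 |

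Only a hold of instillation 1 moves the first sample. The plan's own example, with a week 4 hold, does not show this case.

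**Allowing for windows.** With no hold, BCG 1 is due on day 21 +/- 2 and the boost on day 21 +/- 7. BCG 1 minus boost therefore runs from 19 - 28 = -9 to 23 - 14 = +9 days, so the order is not fixed even then. With one hold of BCG 1, it runs from 26 - 28 = -2 to 30 - 14 = +16 days. On nominal dates it is +7.

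**What 'treatment' means in 10.1.3.** At weeks 0, 11 and 15 the vaccine is the only treatment due. The pre-treatment requirement must therefore cover vaccine doses as well as BCG. A week 3 sample taken after the boost fails it.

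**The case against.** The strongest reply has four parts.

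- **The specified analyses are pre/post.** Sections 14.3.2 and 14.3.3 compare pre-treatment with post-treatment values and name no week 3 or week 8 contrast. The week 0 sample does not move. This stands, and it limits the point. But 10.1.7.2 lists week 3 among the time points to be analysed, and objectives 1.3.7 and 1.3.8 cover all PBMC samples and sera at all time points, so the sample has a planned use.
- **Weeks 11 and 15 are not cancelled.** Section 5.2.3.5 sends the reader back to Section 10.1, and the example's list corresponds to the analysed time points in 10.1.7.2. This also stands. A reader might infer that patients with a hold lose two of six samples, but the documents support only a contradiction over whether those draws are taken.
- **The week 3 case is narrow.** The urinary-symptom trigger in 5.2.3.3 refers to the previous week's instillation, so it cannot apply to BCG 1. If infection is the reason and antibiotics are given, Section 5.5 requires the course to be finished before any vaccine dose. The boost would then wait too, which sits awkwardly with 5.2.3.4 and needs reconciling. A hold for gross hematuria has no such effect, so the sequence remains possible.
- **Tying draws to BCG is deliberate.** Section 5.1.3 times the week 3 and week 8 draws to the start and end of BCG in both arms, which keeps the arms comparable. That is a fair reason to leave the BCG 6 draw where it is. A single hold puts that draw a nominal 14 days after the second boost, and the windows already allow up to 58 - 42 = 16 days without any hold. The reason does not extend to letting the 'week 3' sample follow the boost.

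**Conclusion.** The point holds as a conflict within the protocol, minor in weight. Followed literally, Section 5.2.3.4 can produce a 'week 3' sample taken one or more weeks after the first boost, and its example leaves out two draws required elsewhere. The first result assumes that instillation 1 itself is held and that the boost keeps its planned date.

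The effect is limited to the exploratory immune correlates. Recurrence-free survival, the power calculation, the 49-patient target and the pre-vaccination sample are not affected.

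Two stronger readings are tempting and should be resisted. A reader might estimate how many patients are affected from the TICE BCG toxicity table in Section 8.1.2.1. That table gives adverse-event frequencies, not hold frequencies, and says nothing about holds before the first study instillation, so no count can be given. A reader might also infer that the displaced 'week 3' samples come from patients reacting to BCG, which would confound the immune comparison. At BCG 1 no study BCG has yet been given, so a hold there cannot reflect such a reaction.

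**What to change.** 1. In Sections 5.2.3.4 and 10.1.7.2, state that the PANVAC arm's 'week 3' blood is drawn before BCG 1 or the week 3 PANVAC-F dose, whichever comes first.
2. Add the week 11 and week 15 pre-dose draws to the worked example, so that it reads weeks 0, 3, 9, 11, 15 and 18-21.
3. Leave the BCG 6 blood draw and the urine draws tied to BCG.
4. For draws that move with BCG, including the end-of-study sample, record and use the actual days since the last vaccine dose in the analysis.

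The cost is a few lines of text and one more date variable in an exploratory analysis. No draw is added beyond those already in Section 10.1.3 and Calendar A, and no dose, treatment schedule or hold rule changes. If collection is already complete, item 4 still applies, together with checking actual dates to see which 'week 3' samples preceded the boost.

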5.3 AGENT ADMINISTRATION

Treatment will be administered on an outpatient basis. Reported adverse events and potential risks are described in Section 7. Appropriate dose modifications are described in Section 6. No investigational or commercial agents or therapies other than those described below may be administered with the intent to treat the patient's malignancy.

CTEP IND Agents:

rV-PANVAC™ (vaccinia priming vaccine)
rF-PANVAC™ (fowlpox boosting vaccine)

Other Agents:

Bacillus Calmette-Guerin (BCG) – TICE strain

The administration of the agents is described below based on the treatment arms:

5.3.1 TICE BCG alone arm:

Weeks 3-8

Bacillus Calmette-Guerin (BCG) – TICE strain

- Attenuated live strain of *Mycobacterium bovis*
- Induction course of 6 weekly (+/- 2 days) instillations
- Instillation volume (50 mg in 50 mL sterile saline).
- Dose – 50 mg vial (TICE) is reconstituted in accompanying diluent and then further diluted in sterile, preservative-free saline according to manufacturer guidelines
- Each week, RNs will steriley insert a urethral catheter atraumatically into the subject's bladder and administer the reconstituted BCG. Following instillation of the 50 mL of BCG, the urethral catheter will be removed.

- BCG will then be held in the bladder for 1-2 hours depending on patient ability to hold the medication in the bladder. The patient will then void in a toilet and rinse the toilet with bleach prior to flushing.
- All equipment in contact with BCG will be treated as chemotherapeutic waste and disposed of as such in a MPW container.

5.3.2 TICE BCG + PANVAC™ arm:

Week 0

rV-PANVAC™ (vaccinia priming vaccine) 2×10^8 pfu subcutaneously (+/- 7 days).

Week 3

BCG (+/- 2 days see details above).

rF-PANVAC™ (fowlpox boosting vaccine) 1×10^9 pfu subcutaneously (+/- 7 days).

Weeks 4-6

BCG (+/- 2 days see details above).

Week 7

BCG (+/- 2 days see details above).

rF-PANVAC™ (fowlpox boosting vaccine) 1×10^9 pfu subcutaneously (+/- 7 days).

Week 8

BCG (+/- 2 days see details above).

Week 11

rF-PANVAC™ (fowlpox boosting vaccine) 1×10^9 pfu subcutaneously (+/- 7 days).

Week 15

rF-PANVAC™ (fowlpox boosting vaccine) 1×10^9 pfu subcutaneously (+/- 7 days).

5.3.3 Precautions for the vaccines

- Prior to administration of the drugs, safe-handling precautions should be thoroughly reviewed (see Section 9, precautions and special handling subsections of “Pharmaceutical Information”).
- The proper procedure for disposing the live vaccine is a critical part of drug administration (see Section 9, disposal sections of “Pharmaceutical Information”).

5.4 DOSE LIMITING TOXICITY

TICE BCG will be given in the standard dose and schedule as described above. All toxicities observed will be tabulated by maximum grade per subject. A dose limiting toxicity (DLT) will be any grade 3 or greater adverse effect (AE) by CTCAE v5.0 related to the investigational agent and persisting for more than one week and not improving by routine standard of care. In

addition, any grade 3 or greater AE as per a previously published vaccinia toxicity grading scale³³ related to the investigational agent will also be considered a DLT.

Intravesical BCG therapy can lead to common side effects that are usually self-limited, particularly with dose reduction. These side effects include, but are not limited to, gross hematuria, dysuria, frequency, urgency, bladder spasms, and generalized cystitis. These side effects will not be considered a DLT if it is related to BCG and resolves with BCG dose reduction and/or postponing therapy by 1-2 weeks and treating symptoms with conservative management. In contrast, persistent side effects despite dose reduction/postponing of BCG therapy or the development of systemic BCG infection (aka “BCG-osis”) will be considered a DLT.

Severe adverse events due to local instillation of BCG are uncommon. In a retrospective analysis of 2602 patients reported in 1989, the overall rate of serious complications was less than five percent.³⁴ The most common complication was fever >103°F in 2.9 percent followed in decreasing frequency by:

- Significant hematuria (1 percent)
- Granulomatous prostatitis (0.9 percent)
- Pneumonitis and/or hepatitis (0.7 percent)
- Arthralgia (0.5 percent)
- Epididymitis (0.4 percent)
- Sepsis (0.4 percent)
- Rash (0.3 percent)
- Ureteral obstruction (0.3 percent)
- Contracted bladder (0.2 percent)
- Renal abscess (0.1 percent)
- Cytopenia (0.1 percent)

Systemic sepsis and even death can also develop early following local instillation of BCG. During the initial clinical experience with BCG as an intravesical agent, most cases of sepsis could be traced back to recognized errors in BCG administration such as traumatic catheterization, administration too early after transurethral surgery, or instillation during a concomitant UTI. All these conditions result in physical disruptions in the urothelial blood barrier. Sepsis has been estimated to occur in approximately one in every 15,000 patients treated with intravesical BCG.³⁴ Prompt recognition and administration of multidrug, antibiotic therapy is necessary if true BCG sepsis occurs.

- 5.4.1 For the purpose of protecting subject safety, we implement the following stopping rule for safety monitoring of subjects who receive the combination therapy.
- 5.4.2 If one subject experiences a grade 5 event, thought to be possibly or probably due to the combination therapy (PANVAC + BCG), the study will be stopped. For grade 3 or 4

events probably related to the investigational agent (PANVAC) and persisting for more than one week and not improving by routine standard of care, the study will be stopped according to the stopping rule described in Section 14.

5.4.2.1 The exceptions to what constitute true adverse events/DLTs are previously noted.

5.4.3 Formal dose escalation/Phase I study is not planned as the TICE BCG doses are consistent with standard of care and the TICE BCG is being administered in an intravesical fashion while the PANVAC™ is given subcutaneously and in doses that have been shown to be safe in multiple Phase I and Phase II studies in a variety of different cancers.

5.5 GENERAL CONCOMITANT MEDICATION AND SUPPORTIVE CARE GUIDELINES

For the vaccine administration, anti-emetics and anti-diarrheal agents may be administered as required, but are not anticipated to be needed and should not be used prophylactically on the first cycle. The selection of the specific antiemetic regimen is at the discretion of the treating physician. Antiemetic regimens should not include dexamethasone or other steroids.

Other supportive care with blood components, antibiotics, analgesics, general medical therapy, etc., will be delivered as required. Any subjects taking antibiotics for any reason must complete that course of therapy and be free of evidence of further infection before receiving any dose of vaccine. To avoid blunting of the immune response, we will avoid administering corticosteroids or other immunosuppressive agents unless medically indicated.

Symptomatic anemia should be treated with appropriate red blood cell or erythropoietin support.

Thrombocytopenia should be treated conservatively. In the absence of bleeding or a planned invasive procedure, platelet transfusions should be given for a platelet count below 10,000/mm³. If invasive procedures are planned or the subject develops bleeding, platelet transfusions should be administered in accordance with the standard of practice, usually maintaining a platelet count of >50,000/mm³.

